### **5.6.3 Additional Safety Assessments**

### **5.6.3.1 Clinical laboratory evaluations**

Values outside the reference range will be flagged in the listings. Measurements of laboratory data that are below the limit of quantification (BLQ) will be imputed with half of the lower limit of quantification (LLOQ) in the summary tables and will be reported as BLQ in the listings.

Clinical laboratory (hematology, coagulation, blood chemistry, and urinalysis) parameters are assessed at Screening Visit, Day 1-predose, Day 3, and Day 11.

A serum pregnancy test is performed at Screening Visit and urine pregnancy tests are performed at Day -1, Day 3, and Day 13.

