## **8.15 Day 13**

- Perform urine dipstick pregnancy test for females of childbearing potential only
- Obtain blood samples for safety laboratory assessments
- Obtain vital sign measurements (SBP, DBP, pulse rate, respiratory rate, and body temperature) at 72h ( $\pm 15$ min) postdose
- Perform 12-lead ECG at 72h ( $\pm 15$ min) postdose
- Obtain blood samples for plasma PK at 72h postdose
- Record concomitant medication and medical procedures
- Record AEs

After all scheduled procedures have been performed on Day 13, the subject may be discharged from the clinical unit provided that there are no safety concerns in the opinion of the Investigator.

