### **12.4.2 Clinical laboratory test**

Laboratory variables and changes from Baseline (Day 1 pre-dose assessment) will be descriptively summarized at each time point. Shift tables from Baseline to each post-Baseline time point will be presented. Values outside the reference ranges will be flagged in the listings.

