## **5.6 Safety Analyses**

All safety analyses are conducted for the SS. Safety measurements are summarized at each scheduled time point.

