#### **5.6.3.1.1 Hematology, coagulation, and blood chemistry parameters**

The following parameters are measured:

- **Hematology**

WBC, RBC, hemoglobin, hematocrit, mean corpuscular volume (MCV), mean corpuscular hemoglobin (MCH), mean corpuscular hemoglobin concentration (MCHC), platelet count, lymphocytes\*, monocytes\*, neutrophils\*, eosinophils\*, basophils\*, atypical lymphocyte

\* Variables are summarized on both absolute value and percentage.

- **Coagulation**

Prothrombin Time (PT), International Normalized Ratio (INR), and activated Partial Thromboplastin Time (aPTT).

- **Blood chemistry**

calcium, chloride, creatinine, magnesium, potassium, sodium, glucose, blood urea nitrogen (BUN), aspartate aminotransferase (AST (SGOT)), alkaline phosphatase (ALP), alanine aminotransferase (ALT(SGPT)), gamma-glutamyltransferase (GGT), total bilirubin, lactate dehydrogenase (LDH), total cholesterol, albumin

A summary of the absolute and change from Baseline values for each hematology, coagulation and blood chemistry parameter by scheduled visit will be presented.

Shift from Baseline to the post-Baseline time point (Day 3, Day 11) based on reference range and clinical significance (Normal; Abnormal, Not Clinical Significant; Abnormal, Clinical Significant) is provided for all hematology, coagulation and blood chemistry parameters.

A listing of participants who meet the criteria for potential drug-induced liver injury (PDILI) will be presented together with any additional relevant data collected, including:

- Hy's Law
- ALT
- AST
- Bilirubin
- Symptoms Potentially Associated with Hepatotoxicity: Hepatitis

- Symptoms Potentially Associated with Hepatotoxicity: Hypersensitivity

A figure of time course for serum liver function tests for participants meeting potential Hy's law criteria will be presented.

Hy's law is defined as:  $\geq 3 \times \text{ULN}$  ALT or AST with coexisting  $\geq 2 \times \text{ULN}$  total bilirubin in the absence of  $\geq 2 \times \text{ULN}$  ALP on the same visit.

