#### **5.6.3.1.2 Urinalysis parameters**

The following parameters are measured:

- Urinalysis: pH, bilirubin, glucose, ketones, urobilinogen, protein, nitrite
- Urine Sediment: albumin, bacteria, crystals, RBC, WBC

The number and percentage of participants with each response category for qualitative urinalysis and urine sediment parameters are summarized for the scheduled time points. Percentages are relative to the number of participants with a result for each parameter at each time point.

Shift from Baseline to the post-Baseline time point (Day 3, Day 11) for observed values (negative, trace, 1+, 2+, 3+, etc) is summarized for the above qualitative urinalysis parameters (bilirubin, glucose, ketones, urobilinogen, protein, nitrite).

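### The protocol orders safety laboratory blood on Day 3, Day 11 and Day 13, but the SAP's laboratory schedule and both its shift tables stop at Day 11

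*SAP*

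**What the plan says.** **Protocol.** Section 8.15 (Day 13) carries the instruction "Obtain blood samples for safety laboratory assessments". The same bullet appears in 8.5 (Day 3) and 8.13 (Day 11). Footnote d of Table 5-1 defines the safety laboratory panel as hematology with coagulation, clinical chemistry and urinalysis. For the analysis, section 12.4.2 states: "Shift tables from Baseline to each post-Baseline time point will be presented".

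**SAP.** Section 5.6.3.1 says that hematology, coagulation, chemistry and urinalysis "parameters are assessed at Screening Visit, Day 1-predose, Day 3, and Day 11". The next sentence says that "urine pregnancy tests are performed at Day -1, Day 3, and Day 13". The shift table for blood parameters in 5.6.3.1.1 begins "Shift from Baseline to the post-Baseline time point (Day 3, Day 11" and names no later day. The urinalysis table in 5.6.3.1.2 is worded the same way: "Shift from Baseline to the post-Baseline time point (Day 3, Day 11) for observed values". SAP 6.2, the place for changes to protocol-planned analyses, records none. SAP section 1 gives Protocol Amendment 2 as its basis.

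**The concern.** The two documents give different laboratory schedules after multiple dosing. The visit text has two late laboratory days, Day 11 and Day 13; the SAP has only Day 11. The SAP authors did treat Day 13 as an assessment day, because they carried over the other test that 8.15 lists for that day ("Perform urine dipstick pregnancy test for females of childbearing potential only"). Only the laboratory draw beside it is absent.

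Changes in laboratory parameters are a named safety variable in Protocol 4.3.2. The final dose is given on the morning of Day 10, so a Day 13 sample falls about 72h later. The Day 15 follow-up visit in 8.16 lists no laboratory test, so if the Day 13 draw stands it is the last scheduled one. A site following 8.15 would take blood that the SAP's schedule does not mention, and a programmer following the SAP would leave those results out of the shift tables that 12.4.2 promises. If the draw was not intended, 8.15 orders a sample with no planned place in the analysis.

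**Working it through.** There is no sample-size, power or alpha figure to reproduce. The check compares the post-Baseline laboratory days in the two documents.

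| Source | Day 3 | Day 11 | Day 13 |
|---|---|---|---|
| Protocol 8.5, 8.13, 8.15 (visit text) | ordered | ordered | ordered |
| SAP 5.6.3.1 (assessment days) | named | named | not named |
| SAP 5.6.3.1.1 (blood shift table) | named | named | not named |
| SAP 5.6.3.1.2 (urinalysis shift table) | named | named | not named |

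1. Protocol visit text: {Day 3, Day 11, Day 13}, 3 post-Baseline days.
2. SAP: {Day 3, Day 11}, 2 post-Baseline days.
3. Difference if 8.15 stands: {Day 13}, so 3 − 2 = 1 of 3 days (33%) is absent from the shift tables.
4. In samples, with the 12 planned subjects: 12 × 3 = 36 post-Baseline laboratory sets under the visit text and 12 × 2 = 24 under the SAP. The difference is 12 sets, all from Day 13.
5. Difference if the Day 13 draw is not retained: 2 − 2 = 0 of 2 days absent.
6. Time from the last dose: Day 10 morning to Day 13 morning is 3 × 24h = 72h, which agrees with Protocol 5.1.

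Two limits apply to these inputs. First, the bullets in 8.5, 8.13 and 8.15 speak of blood only. The SAP nevertheless reports urinalysis for Day 3 and Day 11, presumably through footnote d of Table 5-1. The gap is therefore direct for the blood shift table and conditional for the urinalysis table. Second, in the text copy of Table 5-1 available to me, the safety laboratory row shows one mark after Day 3. Column positions are not reliable in that copy, so both the count and the day of that mark need checking in the original. The comparison above uses running text only.

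**The case against.** The strongest reply is that the protocol governs what is collected, and 8.15 is explicit. On that view the collection schedule is not in doubt and the SAP has simply dropped a day. That may well be the answer. However, the SAP sentence states when the parameters are assessed, not merely which days are tabulated, and it gives no Day 13. The running text does not show which document is in error, so I leave that open.

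The second reply is that little is lost, and much of this stands:

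- SAP 5.6 says "Safety measurements are summarized at each scheduled time point", and 5.6.3.1.1 summarizes blood parameters by scheduled visit. Both would arguably keep Day 13 in the descriptive tables, although the visit list in 5.6.3.1 makes it unclear which visits count as scheduled.
- SAP 5.1 provides listings of all documented and derived data, and 5.6.3.1 flags out-of-range values. With 12 subjects, the Day 13 results can be read from a listing.
- The listing for potential drug-induced liver injury and the Hy's Law figure are not limited to Day 3 and Day 11. An abnormal laboratory finding can also be reported as an adverse event.

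These routes limit the harm but do not supply the missing shift-table time point. General wording about scheduled time points does not override a table specification that names its days.

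The point about SAP 6.2 is also conditional: the absence of a declared change is wrong only if the Day 13 draw stands.

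**Conclusion.** The inconsistency is real and nothing in either document reconciles it. Its severity is minor. If the Day 13 draw stands, the shift tables omit 1 of 3 post-Baseline laboratory days, the last one, contrary to Protocol 12.4.2 and without a declared change in SAP 6.2. For urinalysis this also assumes that urine is collected on Day 13. If the draw does not stand, 0 of 2 days are omitted and the error is one bullet in 8.15. Neither case touches the pharmacokinetic results or the primary safety variable, the incidence of treatment-emergent adverse events.

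**What to change.** 1. Reconcile Protocol Table 5-1, 8.13 and 8.15 with SAP 5.6.3.1 on the late laboratory day or days, and state for each day whether urine is collected as well as blood.
2. If Day 13 is retained, add it to the assessment days in SAP 5.6.3.1 and to the blood shift table in 5.6.3.1.1. Add it to the urinalysis shift table in 5.6.3.1.2 only if urine is collected that day.
3. If Day 13 is not retained, remove the laboratory bullet from Protocol 8.15.
4. Record any departure from Protocol 12.4.2 that remains in SAP 6.2.

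The SAP change is one more time point in existing tables and uses blood that 8.15 already orders. On the protocol side it is one bullet or schedule row. If that change is judged significant, Protocol 13.5 requires an amendment with ethics approval.

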#### **5.6.3.1.1 Hematology, coagulation, and blood chemistry parameters**

The following parameters are measured:

- **Hematology**

WBC, RBC, hemoglobin, hematocrit, mean corpuscular volume (MCV), mean corpuscular hemoglobin (MCH), mean corpuscular hemoglobin concentration (MCHC), platelet count, lymphocytes\*, monocytes\*, neutrophils\*, eosinophils\*, basophils\*, atypical lymphocyte

\* Variables are summarized on both absolute value and percentage.

- **Coagulation**

Prothrombin Time (PT), International Normalized Ratio (INR), and activated Partial Thromboplastin Time (aPTT).

- **Blood chemistry**

calcium, chloride, creatinine, magnesium, potassium, sodium, glucose, blood urea nitrogen (BUN), aspartate aminotransferase (AST (SGOT)), alkaline phosphatase (ALP), alanine aminotransferase (ALT(SGPT)), gamma-glutamyltransferase (GGT), total bilirubin, lactate dehydrogenase (LDH), total cholesterol, albumin

A summary of the absolute and change from Baseline values for each hematology, coagulation and blood chemistry parameter by scheduled visit will be presented.

Shift from Baseline to the post-Baseline time point (Day 3, Day 11) based on reference range and clinical significance (Normal; Abnormal, Not Clinical Significant; Abnormal, Clinical Significant) is provided for all hematology, coagulation and blood chemistry parameters.

A listing of participants who meet the criteria for potential drug-induced liver injury (PDILI) will be presented together with any additional relevant data collected, including:

- Hy's Law
- ALT
- AST
- Bilirubin
- Symptoms Potentially Associated with Hepatotoxicity: Hepatitis

- Symptoms Potentially Associated with Hepatotoxicity: Hypersensitivity

A figure of time course for serum liver function tests for participants meeting potential Hy's law criteria will be presented.

Hy's law is defined as:  $\geq 3 \times \text{ULN}$  ALT or AST with coexisting  $\geq 2 \times \text{ULN}$  total bilirubin in the absence of  $\geq 2 \times \text{ULN}$  ALP on the same visit.

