#### **5.6.3.3 Electrocardiograms**

12-lead ECG will be recorded 3 times at 15min [ $\pm 5\text{min}$ ] intervals within 24h before dosing of BRY on Day 1 in order to get representative Baseline. Postdose 12-lead ECG will be recorded 1 time. The individual mean at Baseline will be calculated as raw parameters for descriptive analysis. The definition of Baseline will be the mean of the triplicate measurements predose on Day 1 or Day -1. If there are less than three replicates at Day 1 or Day -1 predose, the mean of the available replicates (predose) will be taken as Baseline.

The following parameters are measured:

- Heart rate, RR interval, PR interval, QRS interval, QT, QTcB\*, QTcF\*\*

\* QT interval corrected for heart rate by Bazett's formula

\*\* QT interval corrected for heart rate by Fridericia's formula

Observed values for the ECG parameters are summarized with descriptive statistics for the scheduled time points. Changes from Baseline for each parameter are summarized for all post-Baseline time points.

For QTcB and QTcF, observed values and their changes from Baseline are summarized based on the classifications of [ $<450$ ,  $450-480$ ,  $480-500$ ,  $\geq 500$  msec] and [ $<30$ ,  $30-60$ ,  $\geq 60$  msec], respectively.

The individual measurements and the mean of the triplicate measurements will be reported in the by-participant listings. The listing will also include the change from Baseline. All ECG findings for the individual measurements will be listed separately.

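### The laboratory shift tables for blood parameters do not separate low from high, so they cannot show the direction of a shift

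*SAP*

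**What the plan says.** **Laboratory shifts.** Protocol 12.4.2 asks for shift tables without naming categories: "Shift tables from Baseline to each post-Baseline time point will be presented". SAP 5.6.3.1.1 supplies the categories, based on reference range and clinical significance: "Normal; Abnormal, Not Clinical Significant; Abnormal, Clinical Significant". The table "is provided for all hematology, coagulation and blood chemistry parameters", for Day 3 and Day 11.

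**Other laboratory output.** SAP 5.6.3.1.1 also plans a numeric summary: "A summary of the absolute and change from Baseline values for each hematology, coagulation and blood chemistry parameter by scheduled visit will be presented". SAP 5.6.3.1 adds that "Values outside the reference range will be flagged in the listings", without saying whether the flag is low or high. SAP 5.1 lists all documented and calculated data. SAP 5.6.3.1.1 has a listing of participants who meet the liver-injury criteria and a time-course figure for those who meet potential Hy's law criteria. Urinalysis has its own category counts and shift tables in SAP 5.6.3.1.2.

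**QTc.** SAP 5.6.3.3 states: "For QTcB and QTcF, observed values and their changes from Baseline are summarized based on the classifications of" <450, 450-480, 480-500 and >=500 msec for observed values, and <30, 30-60 and >=60 msec for changes. It gives no rule for the endpoints of the dash ranges.

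**The concern.** A shift table should show how many participants crossed a reference limit, and which limit. For many laboratory parameters only one side is of safety interest: a rise in ALT or creatinine does not mean the same as a fall, and a fall in neutrophils or platelets does not mean the same as a rise. The planned classes record that a value is abnormal and whether it was judged clinically significant, but not the side. Two things follow. A normal-to-abnormal count is ambiguous, and a participant who goes from below range to above range within the same significance class is counted as unchanged. Changes in laboratory parameters are a named safety variable (Protocol 4.3.2; SAP Table 1-1), so the table should be readable on its own.

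**Working it through.** The plan gives no figure to reproduce here, so the check is one of classification, followed by an illustration of size.

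**1. Scope.** Counting the parameters in SAP 5.6.3.1.1: hematology 14, coagulation 3, chemistry 16. 14 + 3 + 16 = 33.

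**2. What the classes merge.** With direction kept, a value has five states: Low significant, Low not significant, Normal, High not significant, High significant. That gives 5 x 5 = 25 Baseline-to-post moves. The planned table has 3 x 3 = 9 cells.

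| Planned cell | Number of cells | Directional moves in each | Total |
|---|---|---|---|
| Normal to Normal | 1 | 1 | 1 |
| Normal to an abnormal class | 2 | 2 | 4 |
| An abnormal class to Normal | 2 | 2 | 4 |
| An abnormal class to an abnormal class | 4 | 4 | 16 |
| All | 9 | | 25 |

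Eight of the nine cells mix directions. Of the 16 abnormal-to-abnormal moves, 8 cross from one side of the range to the other. Four of those 8 stay in the same significance class and so fall on the diagonal, where they read as no shift.

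**3. Is there another categorical table for blood parameters?** I found none. The liver-injury output is a listing and a figure, limited to participants who meet the criteria. The SAP's abbreviation list includes PCST (possibly clinically significant treatment-emergent), but I found no analysis that uses it.

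**4. Illustrative size.** Assumptions, not in the documents: each reference range leaves 2.5% of healthy values in each tail, and Baseline and post-Baseline values are independent. There are 33 x 12 = 396 parameter-participant pairs per draw.
- Low-to-high: 396 x 0.025 x 0.025 = 0.25 per post-Baseline draw. Adding high-to-low gives 0.50.
- Normal-to-abnormal: 396 x 0.95 x 0.05 = 18.8 per draw, about 9.4 on each side.
- With half the tail (1.25%), these become 2 x 396 x 0.0125 x 0.0125 = 0.12 and 396 x 0.975 x 0.025 = 9.7.

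These figures are probably too high. Positive correlation within a participant lowers both. Inclusion criterion 9 and exclusion criterion 18a screen laboratory values, and 18a excludes ALT, AST or ALP above the upper limit of normal (one confirmatory repeat is allowed).

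**5. QTc bins.** I assigned every whole-number QTc from 380 to 559 msec, and every whole-number change from -60 to +119 msec, to the printed bins.
- Dash ranges read as closed: exactly 480, 500 and +60 fall in two bins. 450 and +30 fall in one.
- Dash ranges read as half-open (lower end included): every value falls in exactly one bin.

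The printed >=500 and >=60 already give 500 and +60 a place. Only 480 lies between two dash ranges with no operator.

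Post-Baseline ECGs per participant: 4 (Single-Dose Period) + 6 (Day 7, Day 10 predose and 1, 2 and 4 h, and 72 h) + 1 (Safety Follow-Up) = 11, so 11 x 12 = 132. The expected number of values at 480, for one correction formula, is 132 x (normal density at 480) x 1 msec. With an assumed mean of 400 and SD of 20 msec this is 132 x 0.000134 / 20 = 0.0009. With a mean of 420 and SD of 25 msec it is 132 x 0.0224 / 25 = 0.12.

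**The case against.** The strongest reply is that the design is deliberate and little is lost. Classifying by clinical significance already separates a trivial low ALT from an important high one. The signed change summaries report mean, SD, median, minimum and maximum for every parameter, so extremes in both directions are visible. The listings show every value. With 12 participants and two post-Baseline draws in the shift table, a reader can find the side of each abnormal value. The protocol names no shift categories, so the SAP does not depart from it, and no objective, primary endpoint or decision rule depends on this table.

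Most of that stands and sets the limits of the point. Three things remain. Means and medians can hide opposite moves, and a minimum or maximum does not count participants who crossed a limit. A listing is not a summary, and the SAP does not say that its flag is directional. Clinical significance is a judgment about importance, not a record of side.

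A reader might infer that low and high values fall into a single abnormal class, or that direction disappears from the safety analysis. The documents support neither: there are two abnormal classes, and direction survives in the change summaries and listings. Nor is the shift table the only categorical laboratory output, since urinalysis has its own; it is the only one for blood parameters. A reader might also infer that the QTc tables will count threshold values twice. That follows only if the dash ranges are closed at both ends. The outer bins fit a half-open convention with no overlap, so this is an unstated endpoint rule and not a demonstrated double count.

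**Conclusion.** The point holds for the shift table alone. As specified, the only planned count of participants changing reference-range status on the 33 blood parameters cannot show direction, and a low-to-high move within one significance class appears as no shift. This conclusion rests on the printed categories and needs no numerical assumption.

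The consequence is modest. Under the stated assumptions, hidden low-high crossings number about 0.1 to 0.5 per draw, and probably fewer. The ambiguous normal-to-abnormal moves are more frequent, but their direction can be recovered elsewhere. Nothing in the pharmacokinetic analysis or the primary safety variable is affected. The change is worth making because it is cheap and makes a required safety table readable on its own.

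The QTc matter is editorial. It concerns a value of exactly 480 msec, with an expected 0.001 to 0.12 occurrences under the assumed means and SDs, and individual ECG values are listed in any case. It would not justify a change by itself.

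**What to change.** **SAP 5.6.3.1.1:** define the shift categories as Low, Normal and High relative to the reference range, with the clinical-significance split kept within Low and within High. This gives at most a 5 x 5 table for each parameter and post-Baseline time point.

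**SAP 5.6.3.3, in the same revision:** write the observed QTc bins as <450, >=450 to <480, >=480 to <500 and >=500 msec, and the change bins as <30, >=30 to <60 and >=60 msec.

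**Cost:** a change to table shells and programming. It uses the values and reference ranges already needed to flag out-of-range results, and the significance judgments the current table already requires. No new data are needed, and the categories stay within Protocol 12.4.2. The downside is slightly larger tables, up to 25 cells instead of 9, many of them empty with 12 participants.
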